### 9.1.3 Sensitivity Analysis of Primary Endpoint

To assess the robustness of the primary efficacy results, the following additional sensitivity analyses will be conducted:

- To evaluate the impact of missing data on the primary endpoint, the primary analysis specified in [Section 9.1.2](#) will be repeated using the ITT Population with Observed Cases (OC), that is, no imputation will be done.
- To evaluate the impact of missing data on the primary endpoint, the primary analysis specified in [Section 9.1.2](#) will be repeated using the ITT Population with baseline observation carried forward (BOCF) method.
- To evaluate the impact of missing data on the primary endpoint, the primary analysis specified in [Section 9.1.2](#) will be repeated using the ITT Population with imputation of the worst case. For the GCRS, the worst case is defined as 3 – Severe Retrusion.

Effective date: 2024-05-29 18:37

Effective

Version: 1.0

Galderma

Protocol number: 43USCH2208

Protocol V4.0

- To evaluate the impact of intercurrent events, the primary analysis specified in [Section 9.1.1](#) will be repeated using the ITT Population with MI but excluding subjects that had a prohibited treatment in or near the treatment area prior to 3 months after last treatment. Subjects with prohibited treatments are defined as subjects with a protocol deviation type of “Prohibited medication or procedure” prior to or on their primary endpoint visit.
- To evaluate the impact of intercurrent events, the primary analysis specified in [Section 9.1.1](#) will be repeated using the ITT Population with MI but excluding subjects who were administered treatment not according to randomization. Subjects who were administered treatment not according to randomization are defined as subjects who were randomized but not treated, subjects whose actual treatment at initial treatment or optional touch-up treatment does not match their planned treatment according to the randomization schedule, or subjects who were treated but not randomized.
- To evaluate the impact of intercurrent events, the primary analysis specified in [Section 9.1.1](#) will be repeated using the ITT Population with MI but excluding subjects that used Hyaluronidase prior to 3 months after last treatment.
- A sensitivity analysis of the primary effectiveness endpoint specified in [Section 9.1.2](#) will be performed based on the PP Population with using observed cases.
- The change from baseline (i.e., number of subjects scored as -3, -2, -1, 0, 1, 2, or 3) will be analyzed as an ordinary outcome, using an Ordinal Logistic Regression. A similar model described for the primary endpoint in [Section 9.1.2](#) will be applied using ordinal logistic regression models. Treatment group (Restylane Lyft with Lidocaine, Juvederm Voluma XC) and Baseline GCRS value (1, 2) will be included in the model as predictors. The reference category for Treatment group will be Restylane Lyft with Lidocaine. The reference category for Baseline GCRS value will be 2. PROC LOGISTIC will be used to generate Odds Ratio point estimates and Wald confidence intervals for Treatment Group and Baseline GCRS value. If the proportional odds assumption is not met, a partial proportional odds model will be used in lieu of a proportional odds model. This partial proportional odds model will be generated using PROC LOGISTIC with an UNEQUALSLOPES option.
- A separate table will present the predicted probabilities of each change from baseline value by treatment. The same PROC LOGISTIC used above, with the addition of the PREDPROBS(I) option will be used to output the predicted probabilities. Using the predicted probabilities, the expected value of the change from baseline will be calculated as:

$$\sum [Predicted\ Probability_i \times Change\ from\ Baseline_i]$$

where  $i$  = Change from Baseline value. The expected value will be presented in the output by treatment.

|   |  |   |
|---|--|---|
| 

GALDERMA

631.1181

 | 

Title

43USCH2208 Statistical Analysis Plan (SAP)

 | 

Doc id

MA-60980

 |
|---|--|---|

Effective date: 2024-05-29 18:37

Effective

Version: 1.0

Galderma

Protocol number: 43USCH2208

Protocol V4.0

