4.3.4 Prohibited concomitant therapies

The following therapies are prohibited during the study because they may interfere with the effectiveness and/or safety assessment of the study product and/or injection procedure:

- Medications that have the potential to prolong bleeding times such as anticoagulants or inhibitors of platelet aggregation (e.g., warfarin, clopidogrel, aspirin, NSAIDs), Omega 3 or Vitamin E should not be used within 2 weeks (i.e., 14 days) before any treatment to avoid increased bruising or bleeding at injection sites.

Omega 3 and Vitamin E are acceptable only as part of a standard multivitamin formulation. COX-2 inhibitors are allowed.

- The study product contains lidocaine, but additional local anesthesia may be used. Lidocaine should, however, be used with caution in subjects receiving other local anesthetics or agents structurally related to amide-type anesthetics, e.g., certain antiarrhythmics, as the systemic toxic effects can be additive.
- Concomitant treatment with chemotherapy, immunosuppressive agents, immunomodulatory therapy (e.g., immunosuppressive monoclonal antibodies, antiviral treatment for hepatitis) is prohibited.
- Systemic steroids (except intranasal/inhaled steroids) or prescription topical steroids (below the level of the horizontal line from subnasale).
- Topical (facial) prescription retinoids below the level of the horizontal line from subnasale including the neck, or systemic retinoids.
- Energy-based aesthetic procedures (e.g., laser, intense pulsed light, radiofrequency and ultrasound) below the level of the horizontal line from subnasale.
- Mechanical (e.g., dermabrasion, needling) or chemical aesthetic procedures (e.g., chemical peel) below the level of the horizontal line from subnasale.
- Treatment with cryotherapy below the level of the horizontal line from subnasale including the neck.
- Lipolytic injections below the level of the horizontal line from subnasale.
- Neurotoxin treatment below the level of the horizontal line from subnasale including the neck.

Effective date: 2023-05-24 22:48

- Treatments below the level of the horizontal line from subnasale including the neck with absorbable or temporary dermal fillers (e.g., collagen, HA products, Calcium Hydroxylapatite, poly L-lactic acid products, etc.).
- Treatments with any permanent filler or implant, lifting threads, or autologous fat in the face.
- Tattoo or piercing interfering with the study injections and/or study assessments.

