- Planned aesthetic facial plastic surgery (e.g., surgery to either the upper or lower lip, facelift, rhinoplasty, facial liposuction etc.) or oral surgery including dental implants, tooth extractions, orthodontia are prohibited.
- Participation in any other clinical study during this study is prohibited.

If a prohibited therapy becomes a necessary treatment for the safety or best interest of the subject, the Sponsor Medical Expert should be notified, time permitting, to discuss possible alternatives prior to administration of a prohibited therapy.

If a subject receives prohibited therapy during the clinical study, the Sponsor should be notified to discuss the pertinence and the modalities for the subject to continue in the clinical study.

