**Table 7. Protocol deviations**

| Deviation   |
|---|
| Any subject that conducts their 3 months after last treatment visit out of window by greater than 21 days or earlier than 7 days                            |
| Any subject not treated according to the assigned treatment.  |
| Any subject that does not have a Blinded Evaluator GCRS onsite live assessment at the primary endpoint visit (3 months after last treatment).               |
| Any subject that does not have an available Baseline (or screening if combined) Blinded Evaluator GCRS onsite live assessment.                              |
| Any subject that does not have grade 1 or 2 on either the Blinded Evaluator or Treating Investigator GCRS onsite live assessment at screening and Baseline. |

Galderma

Protocol number: 43USCH2208

Protocol V4.0

| Deviation  |
|--|
| Any subject with prohibited concomitant treatments/procedures prior to the 3 months after last treatment visit considered to have a substantial impact on the primary efficacy outcome.  |
| Any subject with a prohibited medical history, unstable medical history condition, or medical history condition that worsens prior to the 3 months after last treatment visit considered to have a substantial impact on the primary efficacy outcome. |

Protocol deviations will be presented descriptively. The number and percentage of subjects who have protocol deviations, the total number of deviations and the type of protocol deviation will be summarized using the ITT Population. The above summary of protocol deviations will be repeated by site as well. Protocol deviation listings will be reviewed, and each subject will be classified as belonging to the per-protocol set or not. Exclusions from the PP Population will be identified and documented prior to database lock.

Protocol deviations will be presented in a data listing that will display the visit where the deviation was reported, the date where the deviation occurred, the deviation type and description, the action taken, if it was reported to the Institutional Review Board (IRB) and if the deviation was due to COVID-19. Subjects who are excluded from the PP Population will also be presented in a data listing, along with their reason(s) for exclusion.

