**9.1.1 Primary Effectiveness Estimand**

The primary estimand is the treatment difference of Restylane Lyft with Lidocaine versus a comparator-control for augmentation of the chin region to improve the chin profile by comparing change from baseline in the Blinded Evaluator live assessment of the GCRS at 3 months after last treatment, in all randomized subjects (ITT Population). To address the impact of intercurrent events, sensitivity analyses will be performed separately from the primary endpoint analysis as outlined in [Section 9.1.3](#).

| Primary Endpoint  | Estimand  |   |
|---|---|---|
| Change from baseline in the Blinded Evaluators' live assessment using the GCRS at 3 months after last treatment | Population: all randomized subjects (ITT Population)   |   |
|   | Endpoint: The subject's GCRS based on Blinded Evaluator's live assessment at Month 3 after last treatment  |   |
|   | Intercurrent Events: 
 
1. Use of prohibited treatment in or near the treatment area prior to 3 Months after last treatment.
 
2. Use of Hyaluronidase prior to 3 Months after last treatment.
 
3. Missed visit, early termination, or missing Blinded Evaluator's live assessment of the GCRS leading to missing 3 Months after last treatment observation.
 
4. Administered treatment not according to randomization.
 
5. Subjects who were Lost to Follow Up prior to Visit 4 and re-
 
 | Handling of Intercurrent Events: 
 
1. Use observed response.
 
2. Use observed response.
 
3. Use multiple imputation (MI).
 
4. Use observed response.
 
5. Assume "No Change from Baseline".
 
 |

Confidential

Statistical Analysis Plan Version #1.0

Page 31 of 63

Effective date: 2024-05-29 18:37

Effective

Version: 1.0

Galderma

Protocol number: 43USCH2208

Protocol V4.0

|  |   |  |
|--|---|--|
|  | enrolled after discontinuation.   |  |
|  | Summary measure: Treatment Difference of Restylane Lyft with Lidocaine versus Juvéderm Voluma XC (control) using the GCRS in average change from Baseline. |  |

Note: Intercurrent events are defined as events occurring after treatment initiation that affect either the interpretation or the existence of the measurement associated with the clinical question.

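### The sensitivity analysis for prohibited treatment in or near the chin selects subjects by a broad deviation type, so it removes a superset of the event it names

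*SAP*

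**What the plan says.** The estimand table in SAP 9.1.1 lists intercurrent event 1 as "Use of prohibited treatment in or near the treatment area prior to 3 Months after last treatment" and handles it by using the observed response. The note under that table sets the general condition: "Intercurrent events are defined as events occurring after treatment initiation that affect either the interpretation or the existence of the measurement" tied to the clinical question.

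SAP 9.1.3 then plans to repeat the primary analysis in the ITT population with multiple imputation (MI), leaving out subjects with this event. The sentence announcing the exclusion keeps the area limit. The next sentence, which says how the subjects are found, does not: "Subjects with prohibited treatments are defined as subjects with a protocol deviation type of" *Prohibited medication or procedure*, up to and including the primary endpoint visit.

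Protocol 4.3.4 is the list of what is prohibited. It contains local procedures and products, but also drugs that can prolong bleeding, NSAIDs and aspirin among them, which "should not be used within 2 weeks (i.e., 14 days) before any treatment". It lists chemotherapy, immunosuppressive and immunomodulatory therapy, systemic steroids and systemic retinoids. It ends with "Participation in any other clinical study during this study is prohibited".

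SAP Table 7 removes users of prohibited treatments from the per-protocol (PP) set only where the use is "considered to have a substantial impact on the primary efficacy outcome".

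**The concern.** The primary analysis keeps the observed Month 3 score of a subject who had, say, another filler placed in the chin. The purpose of this sensitivity analysis is to show whether the conclusion depends on that choice. For that, the subjects removed should be those with local non-study treatment.

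A programmer who follows the selection sentence would filter on deviation type and an end date. That filter can also pick up a subject who took an NSAID a few days before the first injection, or a course of systemic steroids. Neither is treatment in or near the chin, and the first also predates treatment initiation. If the result then moves, the reader cannot say whether local treatment or the unrelated exclusions moved it. If it does not move, a small local effect may have been diluted.

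**Working it through.** **1. The three rules side by side**

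| | Event 1 (SAP 9.1.1 and its note) | Selection rule (SAP 9.1.3) | PP exclusion (SAP Table 7) |
|---|---|---|---|
| Area | in or near the treated area | none | none stated |
| Earliest time | after treatment initiation | none | none stated |
| Latest time | before Month 3 after last treatment | on or before the primary endpoint visit | before the Month 3 visit |
| Impact | affects interpretation or existence of the score | none | substantial impact on the primary outcome |

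The selection rule matches the event only on the latest time.

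**2. Items of Protocol 4.3.4 against the named event**

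- Bleeding-time drugs before the first injection: not local, and before treatment initiation. They fail both conditions.
- The same drugs before a touch-up: after initiation, but not local.
- Systemic steroids, systemic retinoids, chemotherapy, immunosuppressants: not local.
- Participation in another study: not in itself a treatment of the chin.
- Filler, neurotoxin or lipolytic injection below the subnasale line: can be local. This is the event intended.

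All of these are prohibited, so all can plausibly be logged under the deviation type. Only the last group fits the event.

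**3. The plan's sample size, reproduced**

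Inputs from SAP 3.2.3: margin 0.5, assumed true difference 0.1 in favour of control, SD 0.7, two-sided 95% CI, power 90%, allocation 2:1.

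Control n = (1.960 + 1.282)² × 0.7² × (1 + 1/2) / (0.5 − 0.1)² = 48.3, rounded up to 49. With 98 on Lyft the total is 147, as stated. 147 / 0.85 = 173, and 174 (116:58) is the next total divisible by three. The stated figures hold.

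**4. Cost in precision of extra exclusions**

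The documents give no rate of prohibited-therapy deviations, so the share removed is an assumption, spread evenly over the arms. All 174 are taken as the starting set, because the analysis uses MI. Imputed scores are treated as observed, which is slightly optimistic.

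SE = 0.7 × √(1/(N/3) + 1/(2N/3)); half-width = 1.96 × SE; power = Φ(0.4/SE − 1.96).

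| Removed | N | 95% CI half-width | Power |
|---|---|---|---|
| 0% | 174 | 0.221 | 94.4% |
| 5% | 165 | 0.226 | 93.4% |
| 10% | 157 | 0.233 | 92.1% |
| 15% | 148 | 0.239 | 90.6% |
| 20% | 139 | 0.247 | 88.8% |

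Removing 15% leaves about the planned 147 evaluable subjects.

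**5. How far the excluded set is diluted**

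Let p be the share of subjects with the local event and q the further share with only a non-local or pre-injection deviation (both assumed). The share of the excluded subjects who have the named event is p/(p + q).

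| p | q = 5% | q = 10% |
|---|---|---|
| 1% | 17% | 9% |
| 3% | 38% | 23% |
| 5% | 50% | 33% |

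If q is 0, the share is 100% and the mismatch has no effect.

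**The case against.** The two sentences in SAP 9.1.3 can be read together: the second defines prohibited treatment, and the first still confines it to the treated area. That reading is fair. It leaves the text ambiguous, gives no rule for judging area, and supplies no start time.

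The documents do not define the deviation types. Washout NSAID use could be logged as an eligibility deviation, in which case the rule would not catch it. This stands, and it is why the point is conditional on coding.

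It is also not certain that the PP set keeps such subjects. The impact criterion in Table 7 is a judgement, and SAP Section 7 says its list is not exhaustive. The most that can be said is that PP may keep them, so on this criterion the ITT sensitivity analysis may be the stricter of the two.

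A reader might infer that this is the only check on local prohibited treatment. The documents do not support that. Table 7 already removes prohibited use with substantial impact, and SAP 9.1.2 requires non-inferiority in both ITT and PP, so an impact-filtered exclusion is part of the decision rule.

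**Conclusion.** The point holds as a mismatch between a named event and the rule that selects it. On its plain wording, and subject to how deviations are coded, the rule removes a superset of the subjects with local prohibited treatment. Under the assumed rates, half or more of those removed would not have the named event. The harm is to interpretation: even at 20% removed, power stays near 89%. The analysis is supportive, and neither the primary analysis nor the decision rule changes.

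Three stronger readings should be resisted.

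- A reader might infer that the analysis does not test the event at all. It does remove subjects with the event, provided their use was logged under this type; it fails to isolate them.
- A reader might infer that the rule breaks randomisation. Under Protocol 8.2 subjects are randomised at the baseline visit just before injection, so drug use in the preceding days comes before randomisation. Removing such subjects alike in both arms mainly costs precision.
- A reader might extend the criticism to the bullet on "excluding subjects that used Hyaluronidase prior to 3 months after last treatment". That exclusion matches intercurrent event 2 as listed, and the primary ITT analysis keeps these subjects with their observed response. If reversed subjects score no change, imputing no change would largely reproduce the primary result.

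**What to change.** In SAP 9.1.3, replace the selection sentence. Exclude subjects with a deviation of this type that (a) is judged before database lock, without regard to treatment arm, to be in or near the treatment area, and (b) occurred after the first study injection and on or before the Month 3 visit. Record the judgement for each deviation reviewed.

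No new data are needed. The deviation listing in SAP Section 7 already carries the date, type and description, and PP exclusions are already documented before lock. The cost is one flag, a few words of SAP text and a short documented review.

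The exclusion itself can stay. Setting the affected score to missing and imputing it is a matter of preference: SAP 3.2.4.1 has no Blinded Evaluator GCRS between Baseline and Month 3, so imputation would draw mainly on baseline covariates and injection volume and should give a similar estimate.

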## 9.2 Secondary Effectiveness Analysis

Secondary effectiveness analysis will be evaluated based on the OC in ITT Population, unless otherwise indicated.

P-values obtained for any endpoint other than the primary will only be provided for ease of interpretation of results. All other secondary effectiveness analyses will be performed descriptively only.

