5.7 Post-trial provisions

In time, the study product will be degraded in the body and additional treatments will be necessary to maintain the aesthetic result.

After the final study visit the Sponsor will not supply any additional treatments to the subjects, even if the result does not persist.

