### 3.2.3 Sample Size Justification

Approximately 174 subjects will be treated in the study, randomized in a 2:1 ratio (116 with Restylane Lyft with Lidocaine: 58 with Juvéderm Voluma XC).

For sample size calculation of 174, it was assumed that the true effectiveness of Restylane Lyft with Lidocaine compared to control treatment assessed by the GCRS is approximately 0.1 point lower. A common standard deviation of 0.7 point was assumed for the treatments. Based on the non-inferiority margin of 0.5, a total sample size of 147 evaluable subjects is then required to show non-inferiority of Restylane Lyft with Lidocaine to the control treatment with a power of 90%, using a two-sided 95% CI for the difference between treatment means.

The GCRS scale is designed so that a complete scale step considers a meaningful clinical difference. A change of up to 0.5 points is not considered clinically important, thus, the non-inferiority margin of 0.5 is chosen. We have estimated the standard deviation from previous studies where the scale GCRS has been used.

Accounting for approximately 15% dropouts and non-evaluable subjects due to protocol deviations at 3 months, a total of approximately 174 subjects will be randomized in the study.

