## 11 Statistical/Analytical Issues

### 11.1 Handling of Missing Data

The number of missing values will be summarized and reported as appropriate in all outputs. Calculations for all questionnaires will follow the methods specified in the specific sections of this SAP for the handling of the data.

For ITT analysis of the change from Baseline based on the Blinded Evaluator's live assessment of GCRS at Month 3 after last treatment (primary endpoint), the analysis will be performed using MI as the primary imputation method. Multiple imputation methods are specified in [Section 11.6](#).

Sensitivity analyses will be performed to evaluate the impact of missing data on the primary endpoint using BOCF, worst case, and observed cases as described in [Section 9.1.3](#).

All other effectiveness endpoints will be evaluated based on the OC in the ITT analysis set. Descriptive statistics of all safety data will be performed on OC in the Safety Population.

Galderma

Protocol number: 43USCH2208

Protocol V4.0

In the event the intensity, relationship, or seriousness of an AE is missing, the most severe value will be assigned. Intensity will be assigned to “Severe”, relationship will be assigned to “Related to Study Product and Study Procedure”, and seriousness will be imputed to SAE.

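### Responder rates at Months 6, 9 and 12 have no rule for scores taken after another chin-area procedure, so they can credit that procedure's effect to the study product

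*SAP*

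**What the plan says.** **Responder definition.** SAP 3.1.2 and 3.2.4.1 call a subject a responder if the Blinded Evaluator GCRS is at least one grade better than Baseline. Neither sets a condition about other chin treatment.

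**Data rule.** SAP 9.2 says "Secondary effectiveness analysis will be evaluated based on the OC in ITT Population, unless otherwise indicated", and SAP 11.1 repeats it: "All other effectiveness endpoints will be evaluated based on the OC in the ITT analysis set". SAP 9.1.3 explains observed cases as analysis without imputation. From these data SAP 9.2.1 reports rates, differences, confidence intervals, Fisher p-values and a graph over time for Months 3, 6, 9 and 12.

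**Where other procedures are handled.** The only visible estimand (SAP 9.1.1, primary endpoint) lists "Use of prohibited treatment in or near the treatment area prior to 3 Months after last treatment". It also lists hyaluronidase use with the same time limit, and keeps the observed response for both. SAP 9.1.3 adds sensitivity analyses that exclude these subjects, again for events before the Month 3 endpoint. SAP 7 and Table 7 direct the per-protocol exclusions at deviations up to and including the Month 3 visit.

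**Whether such subjects stay in.** Protocol 4.3.4 prohibits other fillers, implants, fat and planned facial surgery during the study. If a subject nevertheless receives a prohibited therapy, "the Sponsor should be notified to discuss the pertinence and the modalities for the subject to continue in the clinical study". Protocol 3.5 does not name this among its withdrawal categories.

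**The concern.** The visits after Month 3 show how long the result lasts, and loss of effect is a plausible reason for a subject to seek something else. Under Protocol 5.6 the Blinded Evaluator may not discuss treatment with the subject, so a chin restored by another product is graded as seen. With no rule for that score, the plan as written puts it into the numerator of the study-product responder rate.

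The SAP treats the same events as affecting interpretation when they precede Month 3. It is silent for the following 36 of the 48 follow-up weeks (48 − 12 = 36). At stake is whether the late responder rates and the graph over time describe the study product alone, and whether a reader could tell if they do not.

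**Working it through.** **1. The plan's own figure, to obtain arm sizes.** Inputs from SAP 3.2.3:
- "A common standard deviation of 0.7 point was assumed for the treatments"
- true difference: "assessed by the GCRS is approximately 0.1 point lower"
- margin 0.5, allocation 2:1
- "with a power of 90%, using a two-sided 95% CI for the difference between treatment means"

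Control n = (1 + 1/2) × 0.7² × (1.960 + 1.282)² / (0.5 − 0.1)² = 48.3, rounded up to 49. Test n = 2 × 49 = 98. The total is 147, as stated. Allowing for 15% loss, 147 / 0.85 = 172.9, or 173; the stated 174 also divides by 3 for 2:1. So 98 and 49 are the planned evaluable numbers at Month 3. The documents give no figure for Months 6, 9 or 12.

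**2. Effect on one arm.** Let N be the subjects assessed at a late visit and x those with a response to the study product. Let k be those who lost the effect, had another procedure and now score at least one grade better than Baseline.
- Observed-case rate: (x + k)/N
- Non-response after the procedure: x/N
- Excluding these subjects: x/(N − k)

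The overstatement is exactly k/N. Per subject it is 1/98 = 1.0 point for Lyft and 1/49 = 2.0 points for Voluma. With everyone randomized still observed it would be 1/116 = 0.9 and 1/58 = 1.7 points.

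Illustration with an assumed x = 69 of N = 98:

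| k | Observed case | Non-response rule | Excluded |
|---|---|---|---|
| 1 | 71.4% | 70.4% | 71.1% |
| 2 | 72.4% | 70.4% | 71.9% |
| 5 | 75.5% | 70.4% | 74.2% |
| 10 | 80.6% | 70.4% | 78.4% |

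Exclusion removes only part of the overstatement. At assumed true rates near 50% or 85%, the same k gives the same number of points.

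**3. Effect on the difference.** Assume 69/98 against 34/49, a true difference of 70.4 − 69.4 = +1.0 point. Let about 5% of an arm be affected (5 of 98, 2 of 49).
- Both arms: 74/98 − 36/49 = +2.0 points
- Lyft only: 74/98 − 34/49 = +6.1 points
- Voluma only: 69/98 − 36/49 = −3.1 points

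The sign depends on which arm has more such subjects. The response rates and values of k in steps 2 and 3 are assumptions; the documents give neither.

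**The case against.** The strongest reply is that using the observed score is a recognised strategy (treatment policy), and the SAP adopts it for the primary endpoint. Carrying it to later visits would be consistent, so preferring a composite rule is partly a choice of estimand. This stands in part. However, the SAP does not state the choice for the later visits. The primary endpoint also has exclusion analyses that show how much these events matter, and the later visits have none. The optional per-protocol repeat in SAP 9 would not fill the gap, because the stated focus of its exclusions ends at Month 3.

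Second, the chain of events is long. The procedures are prohibited, the Sponsor may end participation, and a subject who leaves becomes missing rather than a responder. This also stands. A reader might infer that durability is in fact overstated, but the documents support only that it can be. Protocol 5.7 ("In time, the study product will be degraded in the body and additional treatments will be necessary to maintain the aesthetic result") might be read as evidence of re-treatment during follow-up. It sits under post-trial provisions and shows only that loss of effect is expected.

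Third, SAP 9.2 makes these analyses descriptive. Procedures (SAP 8.4), deviations (SAP 7) and responder status (SAP 9.2.1) are already listed by subject. That limits the consequence, but readers would have to assemble the corrected rate themselves.

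Some secondary text is blacked out. The legible parts of SAP 9.2, 9.2.1 and 11.1 state the rule for this endpoint without an exception.

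**Conclusion.** The gap is real and of moderate importance. At Months 6, 9 and 12 a response produced by another procedure can be credited to the study product. Each such subject adds about 1 point to the Lyft rate or 2 points to the Voluma rate, if about 98 and 49 are observed. The total cannot be determined, because the number of such subjects is not given; it may be zero.

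Three stronger readings are not supported:
- **That a true difference in durability is masked, or that one product is favoured.** The shift in the difference can go either way, and nothing in the documents says which arm would have more such subjects.
- **That the primary result is compromised.** The non-inferiority test and sample size rest on Month 3, where these events have a stated rule and sensitivity analyses.
- **That hyaluronidase adds to the overstatement.** Dissolving product would more likely lower the response. The defect there is only that scores after Month 3 have no stated rule.

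Observed-case analysis is not itself the error. The problem is its combination with no intercurrent-event rule after Month 3.

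**What to change.** In SAP 9.2.1, for Months 6, 9 and 12 only:

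1. Add an analysis that counts a subject as a non-responder from the first visit after a prohibited filler, implant, fat or surgical procedure in or near the treatment area. Present it beside the observed-case result.
2. Report the number of affected subjects by arm and visit.
3. State how scores after hyaluronidase are handled, and report those subjects separately.

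Leave Month 3 as it is. Overriding the score there would conflict with the primary estimand, which keeps the observed response.

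**Cost.** No new data and no change to how subjects are managed. Concomitant procedures are collected at every visit (SAP 8.4) and deviations are recorded with type and date (SAP 7). The existing prohibited-treatment definition in SAP 9.1.3 ends at the primary visit and covers any prohibited medication or procedure, so a flag must be derived and reviewed case by case, preferably before database lock. Late responder rates may come out slightly lower. The added rule also counts against the product any subject who still had a response when the other procedure was done, which is a reason to show both results.
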